- Quirynen M, van Steenberghe D Bacterial colonization of the internal part of two-stage implants: An in vivo study. *Clin Oral Impl Res* 1994 5: 239
- Todescan *et al.*, 2002
- van Steenberghe D , Naert I, Jacobs R, Quirynen M. Influence of inflammatory reactions vs. oclusal loading on periimplant marginal bone level. *Advan Dental Res* 1999 13:130-135

OBJECTIVES

General Objective

This prospective, multicenter, randomized-controlled clinical study will evaluate the safety and performance of the T3 implants with a modified implant surface and make comparisons against the legacy Nanotite Certain Tapered Implant System for the amount of alveolar crestal bone loss after the placement of a transmucosal abutment.

Specific objectives include:

1. To document the integration success of all study implants by measuring and documenting implant immobility and resonance frequency assessment for up to 5 years.
2. To assess duration of failure-free performance while supporting restorations for five years
3. To measure and document the radiological changes in peri-implant crestal bone levels.
4. To measure and document insertional torque forces using torque-indicating ratchet wrenches.
5. The enrollment of at least 100 patients (up to 200 implants) within three months.

STUDY DESIGN

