This will be a prospective, randomized-controlled study in which qualified patients with partial edentulism will be treated with at least two dental implants. Implant sites will be randomly assigned to receive either a test (T3 Nanotite Certain Tapered Prevail - BNPT) or control (Nanotite Certain Tapered - NINTxx) implant (80:20 – test – control randomization ratio). All implants will be placed in a single-stage manner using torque-indicating instruments to document the torque-insertion profile. At implant placement surgery test implants will receive Encode healing abutments whereas control implants will be provisioned with prefabricated or standard abutments. For the test group an Encode Level Impression will take place at 10 weeks and individual final abutments and prosthesis placement at 3 months following implant placement surgery. A fixture level impression will be taken for control implants at week 10, followed by final restorations at month 3. All implants will be allowed to integrate without occluding forces and all restorations will be cemented. Resonance frequency assessment procedures will be done at implant placement surgery and at prosthesis insertion. Cumulative success rate and crestal bone regression will be the primary study endpoint. Enrollment will continue until 100 patients have completed final prosthetic treatment at the participating study centers. Additional control cases will be derived from on-going clinical trials of the NINT implants matched with the prospective study control group for baseline variables, restorative type (STR, fixed bridges), and implant dimensions. The additional control cases will bring the test and control groups to a 1:1 ratio and allow for more powerful analyses.

Study (null) hypothesis:

The functional success (survival and success rate) of the T3 implant to maintain integration and support of prostheses in this study will be no different than of the control implant. Moreover there crestal bone changes that take place after placement and loading of the T3 Certain Tapered Prevail (BNPTxxx – test implant) and Certain Tapered (NINTxx - control implant) will be the same.

[figure not shown]
MATERIALS AND METHODS

Implants with similar geometry but with different surface roughness will be evaluated. All implants are titanium root-form dental implants. The test implant has an integrated platform switch feature, whereas the restorative components of the control implant will be matched.

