While all implants are to be placed epicrestal if the depth of the osteotomy is over-prepared (e.g., the depth indicator shows that the osteotomy is 1 mm too deep) the implant should always be fully inserted into the osteotomy. If this results in a subcrestal placement this is preferred to a partially-placed implant. Therefore do not reverse or back-out the implant to have the seating surface epicrestal. Do not reverse or back-out the implant for any reason! It is better to be fully-seated in the osteotomy than to be epicrestal.

7. Proximity to teeth: Do not place an implant any closer than 1.5 mm from the crestal emergence margin of a proximal tooth.
8. Proximity to an adjacent implant: Do not place an implant any closer than 3 mm from the collar margin of a proximal implant.
9. Intra-ridge implant positioning: Please be mindful of placing the implant in the buccal-lingual center of the ridge to prevent loss of wall integrity. Whenever possible, select osteotomy positions that are equally distributed mesial-distally in the treatment region.
10. Conforming to the protocol's osteotomy preparation procedures: The drill sequence that is described in the study protocol is to be followed without exception. Please see the drill sequence chart in the Special Procedures section of this protocol. Do not undersize the osteotomy in soft bone conditions.
11. A case comprises all implants covered with one prosthesis. A case will consist of at least one implant with a crown.
12. Restorative cases will consist of single tooth restorations or unilateral short-span fixed prosthesis (<4implants). A patient can receive the maximum of two cases or 8 implants.
13. Cantilevers and pontics are not allowed in any of the study prostheses.
14. Test and control implants have different provisionalization procedures. A detailed description of the prosthetic procedures is part of the chapter "Specific procedures".
15. Temporary prosthesis are limited to flippers or resin bonded bridges for both test and control implants.

Schedule

Visit:	Follow-up Evaluations					
	1	2	3	4	5	6 - 11
	Screening	Day 0	Day 7	Week 10	Month 3	Months 6, 12, 24; 36; 48; 60

Dental / Medical History	X					
Clinical Evaluations		X	X	X	X	X
Randomization		X				
Implant Surgery		X				
Healing Abutment Placement		X				
Healing Assessment			X			
Impressioning				X		
Final Prosthesis Insertion					X	
Implant Mobility Assessment					X	X
RFA Analysis		X			X	
Radiography	PN	PA			PA	PA

PN = Panoramic radiograph

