After removing the healing abutment place a Type 15 Osstell Smartpeg into the implant and perform a Resonance Frequency Analysis (RFA). Obtain for each study implant an Implant Stability Quotient (ISQ) value. Care will be taken in cleaning and packaging the patient’s Smartpegs to ensure they may be used for subsequent RFA measurements.

Final Abutment and permanent Prosthesis Attachment

Prosthetic parts must be of Biomet 3i origin. Prosthetic procedures will take place no later than three (3) months following implant placement. If a patient has more than one case contributing to the study dataset, all cases must be finished at the same time (during the same visit).

Test Implants: Due to the nature of the Encode Impression System only cement retained crowns/dentures are available. Restorations will be composed of milled patient specific abutments (3i Facility Valencia) and individual crowns/prosthesis (local lab) considering the platform-switch approach.

Control Implants: In order to minimize the variables between the two groups, control implants should as well be restored with cemented prosthesis. The prosthesis type, material and anchorage will be recorded on the appropriate Case Report Form.

Radiography

Periapical radiographs of all study implants will be obtained (be sure to use the fabricated bite block). Only original radiographs will be submitted to Biomet3i. For both, digital and conventional radiography, please name the x-rays as previously described (see visit 2).

Visit 6-11 (Month 6-60) – Follow up - Clinical Evaluation

Clinical Evaluation

An evaluation of the status of the study implants will be done according to the procedures described in the Special Procedures section.

Implant Mobility Assessment

For any implant associated with radiolucency, infection, pain, or neuropathy, a specific attempt will be made to determine implant mobility. The restoration will be removed and a post will be firmly attached to the implant to facilitate an evaluation. Opposing force from two hand instruments (e.g. mirrors) will be applied to the post. Any overt indication of mobility will be recorded as a failure. For all failed implants, a detailed report will be completed and provided to **3i** through the Case Report Form ADE (adverse Dental Event form) and Case Report Form ICF (Implant and Component Failure Form).

Radiography

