A global evaluation of the status of the area where the study implants were placed will be recorded using gingival and plaque indices. The **gingival index** will be ranked as follows: (0) Normal gingiva; (1) Mild inflammation, slight change in color, slight edema, no bleeding on probing; (2) Moderate inflammation, redness, edema and glazing, bleeding on probing; (3) Severe inflammation, marked redness and edema, ulcerations; tendency toward spontaneous bleeding.

The criteria for **plaque index** are as follows: (1) No plaque in gingival area; (2) No plaque visible by the unaided eye, but plaque is made visible on the point of the probe after it has been removed across surface at entrance of gingival crevice; (3) Marginal area is covered with a thin to moderately thick layer of plaque; deposit is visible to the naked eye; (4) Heavy accumulation of soft matter, the thickness of which fills out a niche produced by gingival margin and tooth surface; interdental area is stuffed with soft debris.

EVALUATION CRITERIA

Implant Integration Success

An implant will be considered successful if it is immobile at specific points in time. Additionally, long-term implant success will be achieved when tested with instrument pressure at follow-up evaluations with no evidence of persistent peri-implant radiolucency, no persistent or irreversible signs and symptoms of pain, infection, neuropathies, or paresthesia.

Additionally the correlation of initial stability (as reflected in the Insertion Torque Profile) and clinical success will be assessed. The individual implant will be considered the experimental unit. The Insertion Torque Profiles for failed implants will be compared with those from successful implant cases to determine if this baseline variable is predictive.

Radiological Crestal Bone Level Changes

Bone levels measured at three and six month, and all follow-up intervals from both treatment groups will be compared to those measurements observed at the time of implant placement surgery to derive *changes from baseline* values. Differences between groups will be calculated and used to determine if the crestal bone changes are different between groups. A difference of 5% will be considered relevant.

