- Probably related - an event that follows a known or suspected response pattern, is confirmed by improvement upon stopping or reducing treatment, and cannot be reasonably explained by the known characteristics of the patient's clinical state.
- Definitely related - an event that follows a known or suspected response pattern, is confirmed by improvement upon stopping or reducing treatment, and reappears upon repeated exposure.
- Unknown - relationships for which insufficient information exists.

Failure to use an implant due to improper placement is not an adverse event in the absence of pathology, but is censored data for the survival analysis and must be reported on the Implant Failure Form (ICF).

Medical Adverse Events

Death, serious illness or major trauma, whether implant success is affected or not, is an adverse event and must be reported on the Medical Event form (AME). A medical adverse event will be assessed based on causality (criteria described in dental adverse event section) and severity. Severity criteria are described as follows:

- Mild - the adverse reaction does not interfere in a significant manner with the patient's normal functioning level.
- Moderate - the adverse reaction produces some impairment of functioning but is not hazardous to health; may be uncomfortable.

- Severe - the adverse reaction produces significant impairment of functioning or incapacitation and is a definite hazard to the patient's health; this can lead to 1) death or decreased life expectancy, 2) an immediate life-threatening event, 3) inability to resume usual life pattern, 4) significant disability or incapacity.

STATISTICAL ANALYSES

The primary efficacy parameter will be the duration of implant survival (failure-free utilization or lack of mobility) from implant placement. The fraction of surviving implants and cases at the completion of 1, 2 and 5 years of function will be evaluated. Implant survival differences of >5 % will be considered clinically relevant. Clinical outcomes will be evaluated by clinical signs and symptoms of implant failure and dental and medical events.

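### The protocol contradicts itself on whether every implant, or only one with a listed sign, is tested for mobility after Month 3, and objective 1 claims resonance frequency data to 5 years that the schedule does not contain

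*Combined protocol and SAP*

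**What the plan says.** **Role of mobility in the endpoint.** Under Statistical Analyses: "The primary efficacy parameter will be the duration of implant survival (failure-free utilization or lack of mobility) from implant placement". Study Design names a different primary endpoint: "Cumulative success rate and crestal bone regression will be the primary study endpoint". Success is in turn defined through mobility, under Evaluation Criteria, Implant Integration Success: "An implant will be considered successful if it is immobile at specific points in time". The same paragraph adds that "long-term implant success will be achieved when tested with instrument pressure at follow-up evaluations", together with absence of persistent signs and symptoms.

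**When mobility is to be assessed.** The row "Implant Mobility Assessment" in the Schedule table is marked at Month 3 and in the column for Visits 6-11, with no footnote restricting it. The text for Visits 6-11 under the same name reads: "For any implant associated with radiolucency, infection, pain, or neuropathy, a specific attempt will be made to determine implant mobility". It goes on to describe removing the restoration, attaching a post and applying opposing force with two instruments.

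**Resonance frequency assessment (RFA).** Specific objective 1 is to document integration by "measuring and documenting implant immobility and resonance frequency assessment for up to 5 years". Study Design says: "Resonance frequency assessment procedures will be done at implant placement surgery and at prosthesis insertion". The RFA row of the Schedule agrees with Study Design: Day 0 and Month 3.

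**The concern.** A site has two instructions for the same visits. The Schedule and the success criteria point to a mobility result for every implant at every follow-up visit. The visit text describes a test only for implants that already show one of four signs.

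Under the visit text, a mobile implant with none of those signs is not tested. Unless something else reveals it, it enters the survival analysis as a censored survivor, and it is called a success although the success definition refers to a test it never had. If it is found at a later visit, its failure time is recorded late. Sites that resolve the conflict differently would also produce data of different quality.

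The decision to test then rests on an investigator noticing a sign. Investigators know the assignment, because the card is opened before placement and the abutment and impression procedures differ by arm. The threshold for testing could therefore differ between arms, although nothing in the documents shows that it would.

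The RFA wording is a smaller matter. Objective 1 promises a second measure of integration to 5 years that will not be collected after Month 3.

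**Working it through.** The plan states no figure on this point, so the check sets its sections side by side.

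| Section | Mobility at Visits 6-11 | RFA after Month 3 |
|---|---|---|
| Objectives, no. 1 | Measured and documented up to 5 years | Claimed up to 5 years |
| Study Design | Not stated | None |
| Schedule table | Marked, no condition | None |
| Visit 6-11 text | Only if one of four signs is present | None |
| Implant Integration Success | Instrument-pressure test at follow-up, no condition | Not mentioned |
| Statistical Analyses | Lack of mobility is part of the primary parameter | Not mentioned |

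**Step 1: does mobility matter under both statements of the primary endpoint?** Yes. Statistical Analyses names it directly, as one of two alternatives joined by an or. Study Design uses the success rate, and success is defined by immobility.

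**Step 2: can the sections on mobility be read together?** Only by adding something that is not written. Either the Schedule row silently refers to the conditional section of the same name, in which case the success criterion has no matching test for sign-free implants. Or the visit text describes an extra step for flagged implants, in which case the routine test at Visits 6-11 is nowhere described.

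**Step 3: what else could reveal a sign-free mobile implant?**
- Periapical films of all study implants at each follow-up visit (Visit 6-11, Radiography).
- An examination for any evidence of failure, and an interview on pain, numbness and the comfort, fit and retention of the prosthesis (Special Procedures, Clinical Evaluations).
- A rule that lack of osseointegration counts as failure whether or not pathology is found (Dental Adverse Events).

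These cover every implant, but none is a mobility test. The Special Procedures text ties inspection for radiolucency to signs or symptoms of failure, and the impartial evaluator is described as measuring crestal bone.

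**Step 4: does the protocol foresee non-integration without obvious signs?** Yes. The texts for Day 7, Week 10 and Month 3 provide for a spinning implant without infection or radiolucency, which lacks two of the four triggers.

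**Step 5: RFA.** Scheduled at Day 0 and Month 3, against up to 60 months in objective 1. The Month 3 text asks for the measuring pegs to be kept for later use, but the schedule contains no later measurement.

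**Scale of a single misclassified implant.** This is not an estimate of how many are missed. Inputs: 100 patients, 80:20 allocation and the minimum of two implants each.
- Randomized control implants: 100 × 0.20 × 2 = 40. One implant is 1/40 = 2.5 percentage points.
- Test implants: 100 × 0.80 × 2 = 160. One implant is 1/160 ≈ 0.6 points.

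These are crude proportions that ignore censoring, to be read against the plan's relevance threshold of more than 5%. The control cases added from other trials to reach 1:1 would bring the control figure to about 0.6 as well, but how mobility was tested in those trials is not described.

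**The case against.** The strongest reply is that the visit text describes an escalation and leaves a routine check in place. Month 3 supports this reading, since a mobility score is listed there for all implants and a specific attempt is then described for those with signs. On that view the Schedule and the success criteria govern, and the visit text adds restoration removal for suspect implants. This reading is reasonable, and it is why the finding is a contradiction and not a proven decision to omit routine testing. It does not settle the matter. For Visits 6-11 no general score is listed and no routine test is described, so a site cannot tell what to do with a sign-free implant.

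The reply is right to reject several stronger readings that a reader might infer:

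- *That failure can be detected only after another sign is recorded.* The films, the open-ended examination, the interview and the rule on lack of osseointegration are further routes to a recorded failure.
- *That five-year integration is merely assumed in most implants.* The documents do not say how often the triggering signs occur, and every implant has indirect evidence at each visit.
- *That Month 3 has the same gap.* It has a mobility score without a trigger and a stability reading for each study implant.
- *That radiolucency at Month 3 is scored before its film exists.* This rests on the order of headings alone; no time is set for the film relative to prosthesis attachment.

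RFA also appears in neither the success criteria nor the statistical section, so that mismatch concerns the wording of an objective and leaves the primary analysis untouched.

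**Conclusion.** The point stands as an internal inconsistency that should be fixed. After Month 3 the Schedule and the success criteria call for a mobility assessment without condition, and the only written procedure restricts it to implants with a listed sign. The conflict covers all six follow-up visits and a component of the primary parameter. Taken literally, the visit text lets an untested, sign-free mobile implant count as surviving unless indirect evidence flags it, under assessment by investigators who know the arm. Objective 1 overstates RFA, which ends at Month 3.

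No size can be put on the effect on survival or on the comparison between arms. That would need the failure rate, the share of mobile implants without signs, and how long they stay unnoticed over repeated visits; the documents give none of these. A reader might take an assumed share missed at one visit and apply it to the five-year rate. That would be wrong, because an implant missed at one visit can be found at the next. A difference in detection between arms is possible, but the documents do not show one.

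The conclusion assumes that sites may follow the visit text as written.

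**What to change.** 1. Reword the Visit 6-11 mobility section to agree with the Schedule and with Implant Integration Success. Every study implant in both arms gets an instrument-pressure check with the restoration in place at each of Visits 6-11, recorded as mobile or not mobile.
2. Leave the existing restoration-removal procedure as it is, for the triggers already stated.
3. Report implants under connected crowns separately, because an in-place check there partly tests the prosthesis.
4. Restate objective 1 so that RFA is claimed at placement and Month 3 only.

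The cost is protocol wording, one case report form field and a brief check at visits that already take place, with no extra film or visit. There is a small downside: the in-place check is less sensitive than a test with the restoration removed, especially for connected crowns, and the protocol should say so. Its gain is that every implant has a recorded mobility result at the same visits in both arms.

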The **test implant** surface is fashioned using calcium phosphate grit blasting and then etched using the Osseotite® dual acid-etching (DAE) process that establishes a surface roughness (Sa of about 1.2). The blasted and etched surface is present from the implant apex to 1.5 m from the implant collar above this is the original Osseotite surface (Sa 0.6) to the abutment seating surface. The entire length of the test implant has a discrete crystalline deposition of Calcium Phosphate nanoparticles (DCD). Implant length and diameter will be up to the discretion of the investigator within the limits of the following configurations.

4.0mm (D) x 3.4mm (P)	5.0mm (D) x 4.1mm (P)
BNPT4385	BNPT5485
BNPT4310	BNPT5410
BNPT4311	BNPT5411
BNPT4313	BNPT5413

Like the test implants the **control implants** consist of the same internal connection. The NanoTite Tapered implant (Biomet3i) is a threaded titanium alloy (Ti6Al4V) root-form dental implant featuring an internal connection system and associated restorative components. The Osseotite acid-etched surface is present from the apex to the bottom of the machined collar. To the acid-etched surface is added the NanoTite surface treatment of discrete crystalline depositions of calcium phosphate. These crystals range in length from 20 to about 100 nanometers. Restorations will be constructed using Biomet 3i components.

All implants will be available in diameters of 4 and 5 mm and lengths of 8.5, 10, 11.5, and 13 mm.

Patient Sample

A total of 100 patients will be enrolled in the study. Each qualified study patient will provide at least two implants to the data set. Enrollment will continue for three months or until 100 qualified patients (contributing at least 200 implants) have completed final prosthetic treatment. A qualified patient is one who meets admission criteria and has provided informed consent. Each patient will receive **either** test or control implants. Each patient will be randomly assigned to receive either Test or Control implants.

Patient Numbering

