Secondary efficacy parameters will be prosthesis survival and procedural success. For each patient, survival time after study surgery will be calculated by the duration of failure-free, intervention-free, duration of support of a prosthesis. Implant survival curves will be estimated for the Test and Control treatment group and these will be compared using the Log Rank or Wilcoxon tests. Survival rates at six months (Study Visit 6), one-year (Study Visit 7) and 5 years (visit 11) will be computed for each treatment group, and compared using chi-square. The sample size determinations were based upon survival to the five-year point as a measure of efficacy.

A secondary outcome question of this study is the equivalence in the changes in alveolar crestal bone between the modified implant (T3) and its predecessor the Certain™ implant. In previous studies of Biomet3i implants (Calvo-Guirado 2011, Zetterqvist 2009; Östman et al. 2010), crestal bone change-from-baseline values have ranged from a mean of 0.37 mm to 1.2 mm at the six month (Visit 6) time point. For purposes of this study there will be an assumption that the control implant will have a change-from-baseline mean value of 0.75 mm at the 6 month (Visit 6) time period. To declare equivalence the Test implant system will need to have a crestal bone change-from-baseline mean bone level regression of 0.75 ± 0.15 mm; or to declare superiority a mean value of 0.55 mm or lower. For the functional evaluation of crestal bone regression will be determined for each of the treatment groups at 3 months (Visit 5), six months (Visit 6) and at each of the annual study visits. The significance of these changes from baseline will be evaluated at each time point using a paired t-test or a Wilcoxon signed rank test. At each time point the treatment groups will be compared using the analysis of variance or the blocked Wilcoxon test, as appropriate. Analysis to determine association with other variables will use “exact” rather than “asymptomatic” methods where necessary.

The Test and the Control implants will be considered the experimental units. The influence of the length and diameter of the implants as a covariate on survival will be determined during the analysis. The comparability of the Test and Control treatment groups will be determined with regard to demographic

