variables (including age, gender) and variables relating to the severity of disease (such as existing dental pathology and dental hygiene). For the continuous variables age and evaluations of oral hygiene and the gingival biotype, the groups will be compared using either analysis of variance or blocked Wilcoxon, as appropriate. For the qualitative variables, sex, smoking habit, existing dentition, concomitant conditions, a chi-square contingency table analysis will be used. Analysis to determine association with other variables will use "exact", rather than asymptotic methods where necessary.

All dental and medical events will be tabulated. Treatment groups will be compared using chi-square with regard to the number of patients in each group who experience those events most frequently and are assessed by the investigator as being probably or definitely related to the investigational treatment. Statistical significance will be declared if the two sided p-value is > 0.05 .

Calvo-Guirado JL, Gómez-Moreno G , López-Marí L, Guardia J, Negri B, Martínez-González JM. Crestal bone loss evaluation in osseotite expanded platform implants: a 5-year study. Clin Oral Impl Res 2011 21 MAR 2011
DOI: 10.1111/j.1600-0501.2010.02130.x

Östman PO, Wennerberg A, Albrektsson T. Immediate occlusal loading of NanoTite Prevail implants: a prospective 1-year clinical and radiographic study. Clin Implant Dent Relat Res. 2010 Mar;12(1):39-47.

Records / Data Retention

Case Report Forms (CRFs) will be prepared by 3i for the collection of data. These forms will be used for the entire duration of the study. The original of the completed CRF will continuously be collected by the study monitor for analysis and storage. Only original radiographs (or digital images saved on a disc) will be accepted and maintained by the study sponsor. Investigators will keep a copy of the CRFs and will maintain these records for at least three years.

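### The 5% relevance label for crestal bone differences has no stated base and no link to a test or interval, so chance alone could often earn it

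*Combined protocol and SAP*

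**What the plan says.** Two sections deal with the same outcome.

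- **EVALUATION CRITERIA, Radiological Crestal Bone Level Changes.** Changes from baseline at three months, six months and every later follow-up are compared between groups. The differences are "used to determine if the crestal bone changes are different between groups. A difference of 5% will be considered relevant". The section does not say what the 5% is a percentage of. It names no test, standard error or interval, and it does not refer to the statistical section.
- **STATISTICAL ANALYSES.** Earlier studies are cited in which "crestal bone change-from-baseline values have ranged from a mean of 0.37 mm to 1.2 mm at the six month (Visit 6) time point". For planning, "there will be an assumption that the control implant will have a change-from-baseline mean value of 0.75 mm" at Month 6. Equivalence requires the test group to have a "mean bone level regression of 0.75 ± 0.15 mm; or to declare superiority a mean value of 0.55 mm or lower". For the comparison itself, "At each time point the treatment groups will be compared using the analysis of variance or the blocked Wilcoxon test, as appropriate".

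The only significance rule reads "Statistical significance will be declared if the two sided p-value is > 0.05". It stands in the paragraph on dental and medical events, and its inequality is printed the wrong way round. The documents give no SD for crestal bone change and mention no confidence interval.

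**The concern.** Whether a difference is relevant is judged on a bare point difference. If the threshold is small compared with the sampling error, the label mostly reports noise, in either direction. The label can be applied at seven radiographic visits (Months 3, 6, 12, 24, 36, 48 and 60), and none is singled out for it.

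Bone preservation is in the study title, and STUDY DESIGN counts crestal bone regression in the primary endpoint. A relevant benefit or a relevant harm of the test implant could therefore be reported when there is none. The same result could also meet the plan's own definition of equivalence.

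**Working it through.** **No planned figure to reproduce.** The plan attaches no SD, power or error rate to the 5% criterion. Its sample size is said to rest on five-year survival, without rates or power.

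**Inputs from the documents**
- "A total of 100 patients will be enrolled in the study", with at least two implants each (Patient Sample).
- Allocation is 80:20 by patient (Randomization), taken here as 80 v 20 patients.
- External control cases bring the groups to 1:1 (STUDY DESIGN), taken here as 80 v 80.
- The control mean is 0.75 mm (STATISTICAL ANALYSES).

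**Assumptions, because the documents are silent**
- The 5% is a percentage of the control mean.
- The SD of change is 0.3 to 1.0 mm.
- Each patient has exactly two implants, with a within-patient correlation ρ of 0 to 0.5.
- There is no dropout, and external controls behave like randomised ones.

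**Step 1: the threshold.** 0.05 × 0.75 = 0.0375 mm. Over the cited means of 0.37 to 1.2 mm it would be 0.0185 to 0.060 mm.

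**Step 2: standard error and chance of exceeding the threshold when the implants are identical.**

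SE = SD × √[((1+ρ)/2) × (1/n_T + 1/n_C)]

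P = 2 × [1 − Φ(0.0375/SE)]

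For 80 v 20, √(1/80 + 1/20) = 0.25. For 80 v 80, √(1/80 + 1/80) = 0.158. As an example, SD 0.3, ρ 0, 80 v 20 gives SE = 0.3 × 0.707 × 0.25 = 0.053 mm and P = 48%.

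| SD (mm) | ρ | 80 v 20: SE (mm) | P | 80 v 80: SE (mm) | P |
|---|---|---|---|---|---|
| 0.3 | 0 | 0.053 | 48% | 0.034 | 26% |
| 0.3 | 0.5 | 0.065 | 56% | 0.041 | 36% |
| 0.5 | 0 | 0.088 | 67% | 0.056 | 50% |
| 0.5 | 0.5 | 0.108 | 73% | 0.069 | 58% |
| 1.0 | 0 | 0.177 | 83% | 0.112 | 74% |
| 1.0 | 0.5 | 0.217 | 86% | 0.137 | 78% |

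The threshold is below one standard error in every row except SD 0.3, ρ 0, 80 v 80. With ρ 0, P passes 50% at an SD of about 0.32 mm (80 v 20) or 0.50 mm (80 v 80).

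**Step 3: sensitivity to the assumptions.**
- *Smaller SD.* At SD 0.2 mm, P is 29% to 39% (80 v 20) or 9% to 17% (80 v 80).
- *More implants.* With four per patient, SD 0.4, ρ 0 and 80 v 80, SE = 0.4 × √(0.025/4) = 0.032 mm and P is about 24%.
- *Another base.* If 5% meant 5% of implant length (8.5 to 13 mm, so 0.425 to 0.65 mm), P is at most 9%. That maximum treats each patient as a single observation, at SD 1.0 mm.

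**Step 4: overlap with equivalence.** The equivalence limit is 0.15 mm, which is 0.15/0.75 = 20% of the control mean. The superiority step is 0.75 − 0.55 = 0.20 mm, or 26.7%. If the control mean is 0.75 mm, an observed difference between 0.0375 and 0.15 mm is both relevant and equivalent. At ρ 0, the chance that identical implants fall in that zone is P(>0.0375) − P(>0.15). For SD 0.3, 0.5 and 1.0 mm this gives:
- 80 v 20: 48.0 − 0.5 = 47.5%, 67.1 − 9.0 = 58.1%, 83.2 − 39.6 = 43.6%.
- 80 v 80: 26.4 − 0.0 = 26.4%, 50.2 − 0.7 = 49.5%, 73.7 − 18.0 = 55.7%.

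**Step 5: is 0.0375 mm a usable target?** At 1:1, 80% power and two-sided 0.05, with independent observations, n per arm = 2 × (1.96 + 0.84)² × SD²/0.0375². That is about 1,005 at SD 0.3 mm and 2,791 at SD 0.5 mm.

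**The case against.** The strongest reply is that the 5% is only a label of importance and that the decision belongs to the planned test. The protocol uses the same construction for survival, where a 5% difference is called clinically relevant and log-rank, Wilcoxon and chi-square tests follow. A between-group test is also planned for bone at each visit. Read together, a difference would first have to be significant. At two-sided 0.05, with the printed inequality read as intended, identical implants would be declared different about 5% of the time per visit. Adding the 0.0375 mm condition would change nothing, because even the smallest SE in the table gives 1.96 × 0.0335 = 0.066 mm.

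Much of this stands. A reader might infer that the plan decides by comparing the raw difference with 5%, so that identical implants would usually be found to differ. The documents do not support that. No sentence makes the 5% the decision on its own, and a test is planned. The word *usually* would also need an SD and a base for the percentage that the documents do not give.

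The reply does not dispose of the relevance label. No sentence makes it conditional on the test. The equivalence and superiority criteria in the statistical section are themselves stated as bare means, so judging by an observed mean fits the way the plan is written. The 5% error rate also assumes independent observations, while the plan takes implants as the experimental units. With two implants per patient and ρ 0.5, an analysis that ignores clustering understates the SE by √1.5, so the effective cut-off is 1.96/1.225 = 1.60 and the error about 11%.

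The base of the percentage is uncertain. A percentage of mean bone change is the natural reading, because the sentence concerns differences in those changes and that section does not propose implant length as a base.

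**Conclusion.** The concern holds as a defect of definition with a measurable consequence. The 5% label has no base and is not tied to any measure of uncertainty. On the natural reading it is 0.0375 mm, which is about one standard error or less across the assumed range. Under that reading and the assumptions above, identical implants would exceed it at a single visit in about 48% to 86% of trials in the randomised comparison, or 26% to 78% after the 1:1 top-up. Both ranges fall if the SD is below 0.3 mm or patients contribute more implants.

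These are probabilities of earning the relevance label. They are not the false-positive rate of the planned test, and they do not show that the trial would usually declare two identical implants different. The conflict with the ±0.15 mm equivalence range does not depend on the SD. It needs only the reading of 5% as a share of the control mean and a control mean near 0.75 mm.

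**What to change.** Replace the 5% sentence in the evaluation criteria with one margin in mm, justified by the sponsor and reconciled with the 0.15 mm equivalence limit, and restate the superiority criterion consistently with it. Suggested wording:

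*The between-group difference in mean change from baseline will be reported with a 95% confidence interval that allows for implants clustered within patients. The groups will be called different only if the interval excludes zero, relevantly different only if the whole interval lies beyond the margin, and equivalent only if the whole interval lies within plus or minus the margin. The conclusion rests on Month 6; other visits are descriptive.*

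Month 6 is the visit for which the plan already sets its bone limits. The plan should also state the SD it assumes and print the significance inequality in the intended direction.

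The change costs one paragraph and no new data. The downside is that fewer relevance or equivalence claims can be made. For example, at SD 0.5 mm the half-width of the interval is 1.96 × 0.088 = 0.17 mm (ρ 0) to 1.96 × 0.108 = 0.21 mm (ρ 0.5) for 80 v 20. Equivalence within 0.15 mm would then be out of reach in the randomised comparison. For 80 v 80 it is 0.11 to 0.13 mm, which leaves equivalence possible only when the observed difference is small.
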